2.1 Endpoints

The primary end points are:

- i. OSDI total score.
- ii. Measured lissamine green bulbar conjunctival staining (mm^2).

The secondary end points are symptomatology upon waking (VAS scale).

[REDACTED]

2.2 Hypotheses

The primary hypotheses that to be tested are that:

- i. One-month treatment of moderate to severe dry eye sufferers with an eyedrop / gel combination will reduce overall dry eye symptomatology. The null hypothesis and alternative hypotheses are:

$$H_0: \mu\text{OSDI}_{\text{FU}} \leq \mu\text{OSDI}_{\text{BL}}$$

$$H_1: \mu\text{OSDI}_{\text{FU}} > \mu\text{OSDI}_{\text{BL}}$$

where $\mu\text{OSDI}_{\text{FU}}$ denotes the mean OSDI score at the follow-up visit and $\mu\text{OSDI}_{\text{BL}}$ at the baseline visit.

- ii. One-month treatment of moderate to severe dry eye sufferers with an eyedrop / gel combination will decrease conjunctival staining. The null hypothesis and alternative hypotheses are:

$$H_0: \mu\text{CS}_{\text{FU}} \geq \mu\text{CS}_{\text{BL}}$$

$$H_1: \mu\text{CS}_{\text{FU}} < \mu\text{CS}_{\text{BL}}$$

where μCS_{FU} denotes the mean measured conjunctival staining at the follow-up visit and μCS_{BL} at the baseline visit.

The secondary hypothesis that to be tested is that:

- i. One-month treatment of moderate to severe dry eye sufferers with an eyedrop / gel combination will reduce symptomatology upon waking. The null hypothesis and alternative hypotheses are:

$$H_0: \mu\text{CW}_{\text{FU}} \geq \mu\text{CW}_{\text{BL}}$$

$$H_1: \mu\text{CW}_{\text{FU}} < \mu\text{CW}_{\text{BL}}$$

where μCW_{FU} denotes the mean comfort reported upon waking on a 100-pt VAS scale at the follow-up visit and μCW_{BL} at the baseline visit, where the higher the score the worse is the symptom.

- iii. The improvement in symptomatology will be apparent after the first week of treatment and will improve over the one-month period.

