7.1 Determination of Sample Size

A sample size of 27 achieves 81% power to detect superiority using a one-sided t-test when the OSDI margin of equivalence is 7.5 and the true difference between the baseline and the follow-up value is 10.0, the data being drawn from a single population with a within participant standard deviation of 5.0 and with the significance level (alpha) of the test being set at 0.050. Based upon the intended cohort sample it is proposed to screen 40 participants to have 35 participants enrolled into the investigational phase at the end of Visit 2 to achieve a cohort of 30 participants completing the study as per the protocol.

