The primary variables being continuous variables ideally parametric testing will be carried out. Therefore, if the variables are normality distributed or close to normally distributed before or after transformation allowing parametric analysis parametric statistics the following test will be applied:

OSDI Total Score: A paired t-test approach will be followed. The test will compare the OSDI scores recorded at the two visits (Baseline / Dispensing visit, One-month follow-up visit). The comparisons of the OSDI scores between baseline and one month follow up will be carried out taking 95% as the threshold of significance.

Lissamine green bulbar conjunctival staining: A paired t-test approach will be followed. Lissamine green bulbar conjunctiva staining is recorded and quantified separately for the right and left eyes and for the nasal and temporal bulbar regions; therefore, in order to prevent sample size overestimation by accounting for each measurement the analysis will be carried out on the mean staining of the two zones of the two eyes to have a single data point per visit. The test will compare the mean staining recorded at the two visits (Baseline / Dispensing visit, One-month follow-up visit). The comparisons of the mean staining between baseline and one month follow up will be carried out taking 95% as the threshold of significance.

If the variables cannot be normalized the following test will be applied:

OSDI Total Score: the non-parametric equivalent of the paired t-test is Wilcoxon Rank Test. The test will compare the OSDI scores recorded at the two visits (Baseline / Dispensing visit, One-month follow-up visit). The comparisons of the OSDI scores between baseline and one month follow up will be carried out taking 95% as the threshold of significance.

Lissamine green bulbar conjunctival staining: the non-parametric equivalent of the paired t-test, is Wilcoxon Rank Test. The test will compare the mean staining of the two measurement zones of the two eyes to produce a single data point per visit (Baseline / Dispensing visit, One-month follow-up visit). The comparisons of the mean lissamine green staining between baseline and one month follow up will be carried out taking 95% as the threshold of significance.

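### Two primary endpoints are each tested at an unadjusted 95% level, with no stated testing order, alpha split or rule for primary success

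*SAP*

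**What the plan says.** SAP 2.1 ("The primary end points are") lists two endpoints of equal rank: OSDI total score and measured lissamine green staining in mm². The protocol's synopsis and section 2.4 do the same. SAP 2.2 ("The primary hypotheses that to be tested are that") sets out a separate null and alternative for each.

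The tests in SAP 3.5.2 are also separate. In the linear-model analysis, each endpoint has its own 95% confidence interval. In the simple analysis, the rule for OSDI reads "The comparisons of the OSDI scores between baseline and one month follow up will be carried out taking 95% as the threshold of significance", and the rule for staining reads "The comparisons of the mean staining between baseline and one month follow up will be carried out taking 95% as the threshold of significance". Neither says whether the test is one- or two-sided. SAP 3.5.1 calls for both kinds of analysis for every primary and secondary variable and names neither as decisive.

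The only alpha given is in Protocol 7.1, Determination of Sample Size, and it applies to OSDI alone: "A sample size of 27 achieves 81% power to detect superiority using a one-sided t-test", "with the significance level (alpha) of the test being set at 0.050".

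The available text of the two documents contains no alpha split, no testing order, no rule that both endpoints must succeed, and no definition of study success. Some SAP text is redacted, including a block straight after the endpoint list in 2.1, so the absence is judged on what can be read. The sections where such a rule would normally stand (SAP 2.2, 3.5.1 and 3.5.2) are largely intact.

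**The concern.** With two primary hypotheses, two separate tests and no rule to join them, the plan leaves open what counts as primary success. The reading could be chosen after the results are known: both endpoints, either one, or whichever came out better. If either one is enough, the error rate attached to a primary claim is that of the pair of tests, not the 0.050 in the sample-size section. In practice, a favourable staining result could be reported as primary success when OSDI, the endpoint that set the sample size, has failed.

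**Working it through.** **Inputs.** Two primary endpoints (SAP 2.1). Alpha 0.05, one-sided, n = 27, margin 7.5, true difference 10.0, SD 5.0 (Protocol 7.1, Determination of Sample Size). A 95% level for each endpoint (SAP 3.5.2). The documents give no correlation between the two changes, so a range is assumed.

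**1. The plan's own figure.** Noncentrality = (10.0 − 7.5) / (5.0/√27) = 2.598. A one-sided t-test at 0.05 with 26 degrees of freedom has power 81.2%, which agrees with the stated 81%. The figure takes 5.0 as the SD of the paired difference and concerns OSDI only.

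**2. Both nulls true, either endpoint suffices.** For independent endpoints:

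- each test at one-sided 5%: 1 − 0.95² = 9.75%;
- each test at 2.5% in the favourable direction (a two-sided 95% interval, with only improvement counted): 1 − 0.975² = 4.94%.

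For correlated endpoints, the chance is 1 − P(Z₁ < c, Z₂ < c), with Z₁ and Z₂ standard bivariate normal and c the one-sided critical value:

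| Assumed correlation | 5% per test | Ratio to 5% | 2.5% per test | Ratio to 2.5% |
|---|---|---|---|---|
| 0 | 9.75% | 1.95 | 4.94% | 1.98 |
| 0.3 | 9.3% | 1.86 | 4.8% | 1.91 |
| 0.5 | 8.8% | 1.76 | 4.5% | 1.82 |
| 0.7 | 8.0% | 1.61 | 4.2% | 1.67 |
| 0.9 | 6.8% | 1.36 | 3.5% | 1.41 |

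The ceiling under any dependence is 0.05 + 0.05 = 10%. Simulated one-sided paired t-tests at n = 27 and n = 30 agree: 9.8% at correlation 0, 9.2–9.3% at 0.3 and 8.8–8.9% at 0.5. These figures count one test per endpoint. Choosing between the two analyses in SAP 3.5.1 could add to them.

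**3. What the possible rules would do, at one-sided 5% overall.**

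- *Both must succeed, each at 5%.* With both nulls true and independent endpoints, the joint error is 0.05² = 0.25%; at correlation 0.5 it is about 1.2%. It never exceeds 5%.
- *Fixed sequence, each step at 5%.* A false claim requires rejection of the first true null in the sequence, so the overall error is at most 5%. OSDI power stays at 81.2% for n = 27.
- *Equal split, 2.5% each.* The overall error is at most 5%, but OSDI power falls to 70.6% at n = 27 and 75.4% at n = 30. Reaching 80% takes 34 completers, or 34 × 35/30 = 39.7, so 40 enrolled at the protocol's own completion ratio.

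**4. Whether OSDI can serve as the first step as now written.** SAP 2.2 words the OSDI hypothesis as a reduction in symptoms, but its formal alternative has the follow-up mean above the baseline mean. Protocol 5.3.1 uses a score of 23 or more to mark moderate to severe symptoms, so a higher score is worse and the formal alternative describes worsening. SAP 2.2 also omits the 7.5 margin on which the sample size rests. The margin matters for the first step: at n = 27 and a true difference of 10.0, power is 81.2% against the margin and effectively 100% against zero.

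**The case against.** A reader might infer that the plan's primary error rate exceeds 5%, or is nearly double it, as a matter of fact. The documents do not support that. It requires that either endpoint suffices, that both nulls are true, and that each test is run at 5% in the favourable direction. The SAP's intervals would ordinarily be two-sided. If they decide and only improvement is claimed, the pair's error is 4.2–4.9% for correlations from 0 to 0.7, below 0.050. The one-sided reading is equally open, because the sample-size section and the form of the hypotheses are one-sided. The figure therefore has to be given for both readings. Near-doubling also needs weak correlation: at 0.7 the ratio is about 1.6.

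A reader might also infer that the SAP lets either endpoint carry a primary claim. It does not say so; it states two objectives and leaves success undefined. If each result is reported only against its own hypothesis, each claim keeps its own error rate. This objection stands in part: the defect is that the rule is missing, and the inflation follows from one way of filling the gap.

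Nor does the lack of a power calculation for staining make a false positive there more likely. It bears on the risk of missing a real effect.

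Finally, this is a single-arm, open-label study with entry thresholds on OSDI and staining grade, so scores can move from baseline without any product effect. That may well be the larger threat to a primary claim, and a testing order does nothing about it. It limits the weight of this point but does not remove it, because the plan sets formal hypotheses and an alpha.

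**Conclusion.** The concern holds in conditional form. The available text gives no rule linking two primary tests that are each run at an unadjusted 95% level, and the SAP does not state their sidedness. If either endpoint suffices and both nulls are true, the chance of at least one false primary claim with one-sided 5% tests is 9.75% for independent endpoints, about 8.8% at correlation 0.5 and 8.0% at 0.7. With two-sided 95% intervals and only improvement counted, it is about 4.2–4.9%: within 5% overall, but up to nearly double the 2.5% of each test. The correlations are assumptions. The matter should be settled before the database is closed; it does not invalidate the study.

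**What to change.** The protocol places the SAP before database closure, so the SAP is the document in which to settle this.

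1. **First, correct SAP 2.2.** Reverse the OSDI null and alternative so that they match the stated reduction in symptoms, and reconcile them with the 7.5 margin in the sample-size section by stating whether the test is against the margin or against zero. Otherwise the first step would be passed only on worsening, and its threshold would be undefined.
2. **Then add to SAP 3.5.1:** the sidedness and level of the tests; which of the two analyses is decisive for each endpoint, with the other as supportive; and a fixed sequence. OSDI is tested first at the full level, staining only if OSDI succeeds, and waking comfort only if staining succeeds. After a failed step, later results are descriptive.

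The cost is a short SAP paragraph and the corrected hypotheses. There are no extra participants, and the OSDI power calculation is unchanged. The downside is that staining cannot be formally claimed if OSDI fails.

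A rule that both endpoints must succeed would also control the error, but the chance of success could then not exceed the OSDI power of 81.2% at n = 27, and it would depend on a staining power that the documents do not give. An equal split would lower OSDI power to 70.6% at n = 27. The fixed sequence is the cheaper choice here, though not the only valid one.

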2.3 Hypothesis

The primary hypotheses that will be tested will be that:

- i. One-month treatment of moderate to severe dry eye sufferers with an eyedrop / gel combination will reduce overall dry eye symptomatology;
- ii. One-month treatment of moderate to severe dry eye sufferers with an eyedrop / gel combination will decrease conjunctival staining.

The secondary hypothesis that will be tested will be that:

One-month treatment of moderate to severe dry eye sufferers with an eyedrop / gel combination will reduce symptomatology upon waking.

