5.3 Inclusion and Exclusion Criteria

5.3.1 Inclusion Criteria

There are no requirements as to participant race, gender or occupation. In order to be enrolled, each participant shall meet the following criteria:

- i. At least 18 years old;
- ii. Moderate to severe dry eye symptomatology based up an OSDI score of ≥ 23 ;
- iii. Ocular comfort at waking <65 on 100-point scale;
- iv. Conjunctival staining Grade ≥ 2 (scale 0 to 4) in at least one eye;
- v. Use of eyedrops for the relief of dry eye symptoms for at least one month.
- vi. Have read and understood the Participant Information Sheet;
- vii. Have read, signed and dated the Informed Consent;
- viii. Best corrected visual acuity in each eye of at least 20/25
- ix. Have normal eyes with the exception of the need for visual correction; subjects must be willing to cease contact lens wear for the duration of the study;
- x. Be willing and able to adhere to the instructions set in the clinical protocol and maintain the appointment schedule.

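### SAP 2.2(i) writes the OSDI hypotheses with both inequalities reversed, and the protocol's 81% power belongs to a 7.5-point margin test that the SAP does not contain

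*SAP*

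**What the plan says.** SAP 2.2(i) introduces the first primary hypothesis by saying that treatment "will reduce overall dry eye symptomatology. The null hypothesis and alternative hypotheses are". The null that follows is "H_0: \mu\text{OSDI}_{\text{FU}} \leq \mu\text{OSDI}_{\text{BL" (follow-up mean at or below baseline) and the alternative is "H_1: \mu\text{OSDI}_{\text{FU}} > \mu\text{OSDI}_{\text{BL" (follow-up mean above baseline). In the same section the staining alternative is "H_1: \mu\text{CS}_{\text{FU}} < \mu\text{CS}_{\text{BL" (follow-up below baseline), which agrees with its own sentence about a decrease.

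Protocol 2.3 states the OSDI hypothesis in words only: "One-month treatment of moderate to severe dry eye sufferers with an eyedrop / gel combination will reduce overall dry eye symptomatology". Protocol 5.3.1 fixes the direction of the scale: "Moderate to severe dry eye symptomatology based up an OSDI score of ≥ 23".

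On size, Protocol 7.1 (Determination of Sample Size) says "A sample size of 27 achieves 81% power to detect superiority using a one-sided t-test" and continues "when the OSDI margin of equivalence is 7.5 and the true difference between the baseline and the follow-up value is 10.0", with a within-participant SD of 5.0 and alpha 0.05.

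SAP 3.5.2 compares OSDI at the two visits in two ways. The model analyses use a 95% confidence interval for a least-squares mean difference expressed as a percentage. The simpler analyses use a paired t-test or Wilcoxon test at a 95% threshold. Neither a margin nor the sidedness is stated.

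**The concern.** The SAP is the document that fixes the formal test of each primary endpoint. For OSDI it names the wrong claim: the alternative describes patients getting worse, and the improvement that the trial looks for is part of the null. If this is corrected only after results are known, the correction can look post hoc.

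The second mismatch would remain even with the signs right. The protocol sizes the trial for showing a fall greater than 7.5 points. The SAP pair has no margin, so once corrected it asks only whether OSDI fell at all. These are different success criteria, and the stated power belongs to the first only.

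**Working it through.** **Direction.** An OSDI of 23 or more marks moderate to severe symptoms (Protocol 5.3.1), so higher is worse.

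| Source | Stated in words | Written alternative | Agree? |
|---|---|---|---|
| SAP 2.2(i), OSDI | symptoms reduced | follow-up > baseline | No |
| SAP 2.2(ii), staining | staining decreased | follow-up < baseline | Yes |
| Protocol 2.3, OSDI | symptoms reduced | none given | – |

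Both OSDI signs are reversed and they are consistent with each other, so a single misread symbol is unlikely. Nothing in the available text corrects the pair.

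**Inputs for the power check.** From Protocol 7.1: n = 27, one-sided alpha 0.05, true difference 10.0, margin 7.5, SD 5.0, and 30 intended completers. Assumption: 5.0 is the SD of the change from baseline to follow-up.

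**Reproducing the stated 81%.** This is a paired t-test with power from the non-central t distribution:

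- ncp = (true fall − margin) / SD × √n = (10.0 − 7.5) / 5.0 × √27 = 2.598
- df = 26, one-sided critical t = 1.706, power = **81.2%**
- n = 26 gives 79.8%, so 27 is the smallest n that reaches 80%
- n = 30: ncp = 2.739, power = **84.8%**

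The protocol's figure is correct for the test it describes.

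**The same trial tested against zero.** At n = 27, ncp = 10.0 / 5.0 × √27 = 10.39. Power for a 10-point fall is essentially 100%, one- or two-sided. One-sided power of 81% against zero would correspond to a true fall of 10.0 − 7.5 = 2.5 points, not 10.

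**Smallest observed mean fall that is significant** = margin + critical t × SD / √n. With SD 5.0:

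| Test | n = 27 | n = 30 |
|---|---|---|
| Against zero, one-sided 0.05 | 1.706 × 5/√27 = 1.64 | 1.55 |
| Against zero, two-sided 0.05 | 2.056 × 5/√27 = 1.98 | 1.87 |
| Against 7.5, one-sided 0.05 (Protocol 7.1) | 7.5 + 1.64 = 9.14 | 9.05 |

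An observed fall of 5 points would therefore succeed against zero and fail against the margin.

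**Sensitivity to the SD.** If 5.0 is instead a per-visit SD and the visits are uncorrelated, the SD of the change is 5.0 × √2 = 7.07. One-sided power against 7.5 is then 55.7% at n = 27 and 59.7% at n = 30, which does not match the stated 81%. The n = 27 thresholds become 1.706 × 7.07/√27 = 2.32 and 2.056 × 7.07/√27 = 2.80 against zero, and 7.5 + 2.32 = 9.82 against the margin. The 5-point example still divides the two tests.

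**The written alternative taken literally.** With a true fall of 10 and SD 5.0 at n = 27, a one-sided test for a rise rejects with probability below 1e-15.

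**The case against.** The strongest reply is that the sign error is an erratum without consequence. The words of both documents settle the direction. SAP 3.5.1 defines efficacy as baseline compared with follow-up, and the analyses in SAP 3.5.2 do not refer back to the signs in 2.2. This stands, and it is why the severity is moderate.

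A reader might infer that the trial could never show benefit on OSDI. The documents do not support that. It would be true only of a literal one-sided test of the written alternative, and neither document prescribes one. A two-sided 95% interval or two-sided paired test would show a fall whatever the signs say.

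A reader might also infer that the trial is underpowered, because a two-sided 0.05 test against the 7.5 margin has only 70.6% power at n = 27. Neither document proposes that combination: the protocol pairs the margin with a one-sided test, and the SAP's 95% interval carries no margin. A 95% interval is by convention two-sided, and so stricter than one-sided 0.05. Type I error is therefore not inflated on that route. Only the 95% threshold for the paired test leaves sidedness really unclear.

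Finally, the margin appears only in the sample-size paragraph, and the worded hypotheses in both documents speak of a reduction without a size. It is therefore not shown that 7.5 points was ever meant as the success criterion. That also stands. What remains is that the stated power and the planned test do not belong together, and the documents do not say which governs.

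**Conclusion.** The point holds at moderate severity. SAP 2.2(i) is wrong as written: both OSDI inequalities contradict the sentence above them, Protocol 2.3 and the direction of the scale. The error does not put the result at risk under a two-sided reading of SAP 3.5.2.

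The mismatch over the margin is separate and has a measurable size. The 81% is right for the protocol's one-sided margin test but does not describe the SAP's comparison, for which power at a 10-point fall is essentially 100%. The observed fall needed at n = 27 is about 1.6 to 2.0 points against zero and about 9.1 points for the protocol's test. These figures assume that 5.0 is the SD of the change, the reading that reproduces the stated power. Under the 7.07 reading, the contrast is about 2.3 to 2.8 against 9.8.

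**What to change.** Before database closure:

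1. In SAP 2.2(i), write H0: mean OSDI at follow-up ≥ baseline and H1: mean OSDI at follow-up < baseline, and add that a higher OSDI is worse.
2. Reconcile Protocol 7.1 (Determination of Sample Size) with SAP 2.2 and 3.5.2 by one of two routes, and state the sidedness and alpha of the OSDI test in either case.
   - **Keep the test against zero.** State that the 81% power was calculated for a different test and does not describe this one.
   - **Adopt the margin.** Write H0: mean fall ≤ 7.5 and H1: mean fall > 7.5, in place of the zero-difference pair in item 1. Test it one-sided at 0.05, so that success means the lower limit of the two-sided 90% interval for the fall exceeds 7.5. This must be done on the untransformed OSDI point scale. The percentage difference in SAP 3.5.2, and any interval on the square-root, log or inverse scale allowed by SAP 3.3, cannot be compared directly with 7.5 points.

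The cost is two signs and a sentence in SAP 2.2, and one or two sentences in SAP 3.5.2. If the margin is adopted, the pair in 2.2 is rewritten instead. No data, participants or time are added.

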2.3 Study population

The initial study population is to include up to 40 screened participants to have 35 participants enrolled into the investigational phase and to achieve a cohort of 30 participants completing the study.

The inclusion criteria include the following:

- i. Age at least 18 years;
- ii. OSDI score of ≥ 23 ;
- iii. Ocular comfort at waking <65 on 100-point scale;
- iv. Conjunctival staining Grade ≥ 2 (scale 0 to 4) in at least one eye;
- v. Use of eyedrops for the relief of dry eye symptoms for at least one month.

